### 6.6.3 Mitigation plans for specific AEs

Based on experience with other BioNTech RNA-based vaccines and published data from other RNA-based vaccines, it is anticipated that subjects may experience TEAEs of flu-like symptomatology following the administration of RNA vaccines due to the mechanism of action of RNA vaccines. This may include fever, chills, rigors, tachycardia, arthralgia, myalgia, headache, nausea. Treatment of these events is dependent on the discretion of the investigators; however, the following management suggestions are provided:

- Treat fever with acetaminophen or NSAIDs with a dose per trial site recommendation.
- After the first occurrence of flu-like symptomatology, subjects can be treated with standard therapeutic dose of acetaminophen, or NSAIDs, starting at least 2 h after the immunization.
- Corticosteroids should be avoided as either prophylaxis or treatment as it counteracts the effects of immunization.
- Ensure adequate hydration of trial subjects on the day of immunization. Consider administering fluids (e.g., water for drinking, 0.5 to 1.0 L) within approximately 2 h following the immunization per trial site standard.

If subjects experience enhanced respiratory disease or progression of flu-like symptomatology, such as non-resolution of the symptoms after 7 d, symptom kinetics that are inconsistent with a relationship to RNA immunization, additional diagnostic measures should be considered and the Medical Monitor should be informed.

### 6.6.4 Safety stopping criteria

See Section 6.6.1 for the list of events that must prompt discontinuation for the individual subjects.

The SRC will review and evaluate the collected safety data periodically during the trial (see Section 10.1.5 for details). A decision to stop treatment for an individual subject or to terminate the trial may be taken if safety concerns are identified by the SRC.

Suspected unexpected serious adverse reactions (SUSARs) will immediately be reviewed by the SRC. They will trigger a temporary stop of IMP administration to new subjects in the respective dose level cohort for that vaccine until the SRC recommendation to continue or to permanently stop IMP administration of new subjects in the respective dose level cohort for that vaccine.

Guidance for discontinuation of trial treatment is provided in Section 7.1.

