- If the dosing in these subjects was considered to be safe and well tolerated by the investigator after 24±2 h observation on site, a 4 further subjects will be dosed (with intervals of at least 30 min between subjects).
- If the dosing in these 4 subjects was considered to be safe and well tolerated by the investigator based on 48 h data (24±2 h observation on site and phone interview for assessment 48±2 h after immunization; in addition to the available 48 h data from the sentinel subjects):
  - The remaining 6 subjects in the group will be dosed (with intervals of at least 30 min between subjects).
  - If approved by the SRC, the next planned escalation dose (see Table 1) will be initiated. The data assessed by the SRC comprises 48 h data for 6 subjects including observation on site, short summary of phone interview (including statement about diary reports), vital signs, investigator reported local and systemic reactions, TEAEs, solicited local & systemic reactions, blood/clinical laboratory data, and brief physical examination outcome.

The maximum allowed dose for each vaccine candidate is defined in Table 1.

Clinical Trial Protocol including Amendments Nos. 01 to 09 BNT162-01 Page 52 of 113 Version: 13.0 Date: 12 JAN 2022

For the planned dose de-escalation cohorts, 12 subjects may be dosed on one day (with intervals of at least 30 min between subjects). The doses in these cohorts in younger adults must be lower than doses that have shown acceptable tolerability in younger adults (based on the data from 12 subjects up until 48 h after the first dose). The same dose will not be administered twice, i.e., in two cohorts.

For BNT162b1 and BNT162b2, administration of the planned 10 µg dose in older subjects (Cohort 8) may start once at least a 30 µg dose has shown acceptable tolerability in younger adults (based on the data from 12 subjects up until 48 h after the boost dose).

The dose in Cohort 8 must also be confirmed by the SRC. In Cohort 8, 12 subjects will be dosed using a sentinel dosing/subject staggering (2-4-6) process with intervals of at least 1 h between the first 6 subjects and then at least 30 min intervals for the remaining 6 subjects.

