### 4.2 Scientific rationale for the trial design

The trial design is based on the sponsor's experience with trials of this type and other published trials for vaccine development.

The chosen trial design reflects discussion and advice from the PEI obtained in two scientific advice meetings held in February and March 2020. At these meetings, the PEI supported the high-level design of this trial, specifically the staggered approach, single dose (single immunization dose) and P/B testing, conditional to performance of lower dose exploration if appropriate and re-consideration of the dose regimens for Part B if appropriate.

Part A of the trial is designed as a classical dose escalation, investigating the dose range which is most likely to be well tolerated and induce a virus neutralizing response. To ensure trial subject safety, a staggered approach has been chosen starting with a defined low standard dose. Use of the overlapping escalating doses in Cohorts 1 to 3, i.e., progression to initiation of dosing at the next higher dose when data is available for 6 of 12 trial subjects per group, allows a faster dose escalation while ensuring trial subject safety.

Trial subjects in Cohort 1 (with the FIH immunization), will be immunized using a sentinel dosing/staggering of subjects (EMA 2017 guidance "Strategies to Identify and Mitigate Risks for First-in-Human and Early Clinical Trials with Investigational Medicinal Products").

Clinical Trial Protocol including Amendments Nos. 01 to 09 BNT162-01 Page 55 of 113 Version: 13.0 Date: 12 JAN 2022

The expansion cohorts (Cohorts 11 to 13) are designed to be complementary to the ongoing global Phase I/II/III trial BNT162-02/C4591001 (NCT04368728), to demonstrate clinical efficacy and safety for two 30 µg BNT162b2 doses given ~21 d apart, which enrolled over 40,000 subjects. This Phase I/II/III trial does not include the detailed immunogenicity assessments needed to better understand the mode-of-action of the vaccine and approaches for potential improvements, e.g., in defined populations (by age, gender, immunocompromised status, certain ethnicity-associated HLA, etc.). This trial will therefore include such immunogenicity assessments, including detailed characterization of immune responses to BNT162b2 in respect of binding antibodies, neutralizing antibodies, and cell-mediated immunity (CMI), including evaluation of CD4 and CD8 T-cell responses.

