### 6.6.1 Dose limiting toxicity

### Applicable to dose ranging cohorts only

During the time of enrollment into a given dose escalation cohort in Part A, if any of the following events occur, it will be considered an individual dose limiting toxicity and further dosing in that cohort will be stopped:

- Anaphylactic reaction considered related.
- Generalized urticaria considered related.
- Four trial subjects in that cohort with any severe unsolicited local event, if considered related and not manageable with simple measures (e.g., cooling, analgesia, nonsteroidal anti-inflammatory drugs [NSAIDs]).
- AEs within 7 d of vaccination assessed by the investigator to be potentially lifethreatening (Grade 4) and that are possibly related, or for which there is no alternative, plausible, attributable cause.
- Any systemic SAE within 7 d of vaccination that is assessed by the investigator as possibly related, or for which there is no alternative, plausible, attributable cause.
- Any fever >40.0°C (>104.0°F) within 7 d of vaccination considered related and confirmed by an investigator or medically qualified person.
- Two trial subjects (at any dose level) with the same or similar severe (Grade 3 or higher) AE (including reactogenicity reported as AEs and clinically significant laboratory abnormalities) within 7 d of vaccination, considered related, or for which there is no alternative, plausible, attributable cause (for severity grading of AEs see Section 10.3.1.7).

Page 66 of 113 Version: 13.0 Date: 12 JAN 2022

For the cohorts with BNT162c2 P/B dosing, dosing with the boost dose will only start after SRC assessment of Day 28 safety data (solicited and unsolicited) for the cohort testing BNT162c2 (SD).

Approval from the SRC will be required prior to any further dosing in the affected cohort. The SRC may call for the opening of a lower dose level cohort.

The same events will prompt IMP discontinuation for individual subjects as described in Section 6.6.4. Tasks connected to the discontinuation of IMP are described in Section 7.1.

The above guidance regulates how potential dose limiting toxicities may influence the decisions to further enroll trial subjects in any cohort. These decisions are taken by the SRC based on the 48 h safety data from the first 6 subjects of each cohort (see Section 4.1). Due to the staggered sentinel dosing design, subjects will have been followed for 4 d for the sentinel subjects when this SRC decision is made.

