The above guidance also regulates how potential dose limiting toxicities may influence the decisions to enroll subjects into the next cohort for that vaccine, i.e., to progress to the next cohort. These decisions are taken by the SRC based on the 48 h safety data from all 12 subjects of each cohort (see Section 4.1). Due to the staggered sentinel dosing design, subjects will have been followed for 6 d for the sentinel subjects when this SRC decision is made.

The sum of the above events occurring at any time during the trial conduct (i.e., not just with 7 d of vaccination) will be used for the overall assessment of the candidate vaccine safety profile, i.e., to assess whether any of the observed side effects are possibly linked to vaccination.

The assessment of dose limiting toxicity should be done consistently for all subjects treated with the same treatment and dose.

In addition to data entry in the CRF, dose limiting toxicities (DLTs) will be reported within 24 h via a SAE Report Form as described in Section 10.3.1.10 and forwarded to the safety contacts listed in the same section.

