### 6.6.2 Dose modification guidance/rules

### Part A

See Section 10.1.5 for the data set upon which SRC decisions described below for Part A are made.

- The decision to test reduced or intermediate doses will be made for each vaccine independently.
- Any proposal to alter the planned escalation dose, or to test an additional deescalation dose, must be approved by the SRC.

Dose escalation:

• Dose escalation will only continue if the previous dose was considered safe and well tolerated by the SRC.

BioNTech SE	Clinical Trial Protocol	Page 67 of 113
	including Amendments Nos. 01 to 09	Version: 13.0
Confidential	BNT162-01	Date: 12 JAN 2022

• Any proposal to alter the planned escalation doses must be approved by the SRC.

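### The automatic SUSAR hold covers the dose cohort of the event but not an already open higher-dose cohort of the same vaccine

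*Protocol*

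**What the plan says.** Protocol Section 6.6.4 provides two things after a SUSAR. The first is review: "Suspected unexpected serious adverse reactions (SUSARs) will immediately be reviewed by the SRC". The second is an automatic hold: "They will trigger a temporary stop of IMP administration to new subjects in the respective dose level cohort for that vaccine". The SRC recommendation that ends the hold is limited to the same cohort.

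Escalation overlaps by design. Section 4.1 (dose ranging cohorts) lets the next dose start on SRC approval, at the same step as the last 6 subjects of the current cohort: "The data assessed by the SRC comprises 48 h data for 6 subjects". Section 4.2 gives the reason: "Use of the overlapping escalating doses in Cohorts 1 to 3, i.e., progression to initiation of dosing at the next higher dose", once data exist for 6 of the 12 subjects. Section 6.6.1 is stricter on moving to the next cohort: "These decisions are taken by the SRC based on the 48 h safety data from all 12 subjects of each cohort". Section 6.6.2 adds: "Dose escalation will only continue if the previous dose was considered safe and well tolerated by the SRC".

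The DLT rules in Section 6.6.1 count a possibly related systemic SAE within 7 days of vaccination as a DLT. They stop dosing in one cohort and require SRC approval before dosing resumes in the affected cohort. Section 7.1 requires IMP administration to stop after a DLT and calls for an unscheduled SRC analysis. It does not say which cohorts stop.

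**The concern.** Dose escalation presumes that risk may rise with dose. After a SUSAR at a lower dose, the automatic hold protects new subjects at that dose, while new subjects at a higher dose of the same vaccine may still be primed until the SRC acts. The sponsor included an automatic hold in addition to prompt review, so it did not mean to rely on review alone. The narrow scope leaves the higher dose to review alone. At stake are the prime doses given at the higher dose between recognition of the SUSAR and the SRC decision.

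**Working it through.** The plan gives no figure for this rule, so the check is of text and then timing.

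**1. Does other text pause the higher-dose cohort?**

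| Provision | Effect on an open higher-dose cohort |
|---|---|
| 6.6.4, SUSAR hold | None; limited to the dose cohort of the event |
| 6.6.4, immediate SRC review | SRC can act; no time in hours is given |
| 6.6.2, escalation only if the previous dose was judged safe | Governs opening; for an open cohort that decision is already made |
| 4.1, ad hoc SRC review before further doses of a construct | Optional |
| 4.1, observation prolonged by 24 h | Optional |
| 2.3.1 and 10.1.5, observation to Day 7 in later cohorts | Optional |
| 6.6.1, DLT stop | One cohort; unclear whether it is the one being enrolled or the one with the event |
| 7.1, DLT stop | Mandatory, but no scope stated |

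A SUSAR that occurs more than 7 days after vaccination need not meet the 6.6.1 SAE criterion at all.

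**2. Can the cohorts overlap in time?** The 2-4-6 stagger is placed on days 1, 2 and 4. Let the higher-dose cohort open on day D, with blocks of 2, 4 and 6 on D, D+1 and D+3. Section 6.6.1 dates a decision on 6 subjects thus: "subjects will have been followed for 4 d for the sentinel subjects when this SRC decision is made". That gives D = 4 or 5. For 12 subjects it says: "subjects will have been followed for 6 d for the sentinel subjects when this SRC decision is made". That gives D = 6 or 7. The first lower-dose subjects complete 7 days on day 8, so under either rule no lower-dose subject has done so at opening.

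**3. How many subjects fall in the gap?** Once the cohort is open, the remaining blocks (4 at D+1, 6 at D+3) are 2 days apart. A delay of 1 to 2 days therefore catches at most one of them, so at most 6 subjects.

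**4. Upper illustration.** Assume that a SUSAR occurs and that its onset is uniform over 12 x 7 = 84 lower-dose subject-days. Count only onsets after opening that are followed by a higher-dose prime before the SRC decides. Subjects at risk number 12 on days 4-8, 10 on days 8-9 and 6 on days 9-11. With a decision 1 day after onset, the onsets that count lie in (D, D+1] and (D+2, D+3]; with 2 days, in (D, D+3].

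| D | Decision after 1 d | Decision after 2 d |
|---|---|---|
| 4 or 5 | (12+12)/84 = 29% | (12+12+12)/84 = 43% |
| 6 | (12+10)/84 = 26% | (12+12+10)/84 = 40% |
| 7 | (12+6)/84 = 21% | (12+10+6)/84 = 33% |
| 8 | (10+6)/84 = 19% | (10+6+6)/84 = 26% |
| 11 | 0% | 0% |

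**5. Sensitivity.** If all onsets fall within 48 h of dosing, there are 12 x 2 = 24 subject-days, and only the 6 subjects dosed on day 4 are at risk after opening. D = 4 gives 6/24 = 25% (1 d) and 12/24 = 50% (2 d). D = 5 gives 6/24 = 25% for either delay. D = 6 or later gives 0%.

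All these shares run from onset. A hold can act only from recognition, so they overstate what a wider hold would avert.

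**The case against.** **The DLT rules already cover most of this.** A systemic SUSAR within 7 days is also a DLT, which triggers the Section 7.1 stop and an unscheduled SRC analysis. If the cohort in 6.6.1 is read as the one being enrolled, or the 7.1 stop as applying to the whole vaccine, the gap closes for these events. This carries weight, but neither reading is secured by the text, and 6.6.1 asks for SRC approval only for the affected cohort.

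**The interval is short and partly unavoidable.** Investigators have 24 h from awareness to report an SAE (Sections 10.3.1.6 and 10.3.1.10). In the 1-day case, recognition could take up the whole interval. Section 2.3.1 describes onset of reported TEAEs as typically within the first 24 h, although SUSARs could differ. With onsets within 48 h and the 12-subject rule, the share is zero. This stands and limits the size of the point.

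**Little dosing may remain.** Section 10.10.6 records that all first-in-human cohorts are complete, and version 13.0 changes only follow-up in Cohorts 11 to 13 (Section 10.10.10). For BNT162a1 the starting dose is also the maximum (Table 1, note b). This stands too. The rule remains live on paper because Table 1 still lists higher doses subject to SRC approval, such as 4C, 7C, 4E and 7E.

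**A cohort-level hold with immediate review is a defensible design choice.** It is, which is why this is offered as an improvement and not as an error.

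**Conclusion.** The point holds in a narrow form. The automatic SUSAR hold stops at the dose cohort of the event, and no other provision clearly pauses new subjects in an open higher-dose cohort of the same vaccine before the SRC decides. For a delay of 1 to 2 days, the exposure is at most one block of up to 6 subjects. It is close to zero with a same-day decision, and nil if no dose ranging escalation is open or resumes. Severity is minor.

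A reader might infer that 19% to 43% of lower-dose SUSARs would be followed by an avoidable higher-dose prime. The documents do not support that. They give neither an onset distribution for SUSARs nor an SRC decision time, and the shares are counted from onset. How often a SUSAR occurs cannot be taken from the documents either. A reader might also infer that higher-dose subjects are unprotected. They are not: SRC review is immediate, and the SRC may stop an individual subject's treatment or terminate the trial.

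**What to change.** In Section 6.6.4, change the trigger sentence only, for example: *A SUSAR pauses IMP administration to new subjects at the dose level of the event and in every open cohort of the same vaccine at a higher dose, until the SRC has given its recommendation for each of these cohorts.* Separate recommendations let the SRC release one cohort without the other. Lower-dose cohorts are unaffected.

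Two clarifications are optional. Sections 6.6.1 and 7.1 should state which cohort stops when the two-subject DLT criterion, which counts across dose levels, is met by subjects in different cohorts. They should also be reconciled on second vaccinations: 7.1 allows them during the review, while 6.6.1 requires SRC approval before any dosing resumes in the affected cohort. An automatic pause of all higher doses after every DLT is not proposed; that is a broader and debatable change.

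The cost is one sentence in the protocol, and in the SRC charter if it repeats the rule. No visits, staff or data are added. The downside is that an open higher-dose cohort waits for an SRC review that is already mandatory and immediate.

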## 6.7 Treatment after the end of the trial

Not applicable.

## 7 DISCONTINUATION OF TRIAL TREATMENT AND TRIAL SUBJECT DISCONTINUATION/WITHDRAWAL

## 7.1 Discontinuation of trial treatment

In rare instances, it may be necessary for a trial subject to permanently discontinue IMP administration (i.e., to not receive the boost dose for groups with P/B regimens). If IMP administration is definitively discontinued, the trial subject will remain in the trial to be evaluated for safety, i.e., subjects should still complete all assessments planned in the SoA (Section 1.3).

IMP administration must be stopped if dose limiting toxicities described in Section 6.6.1 are observed.

If any of the above are observed, an unscheduled safety analysis by the SRC will be required. Trial subjects who tolerated initial vaccinations will be allowed to receive a second vaccination during this time.

In the event of discontinuation of trial treatment, it must be documented on the appropriate CRF/in the medical records whether the participant is discontinuing further receipt of trial treatment or also from trial procedures, post-treatment follow-up, and/or future collection of additional information.

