#### Table 1: Dose ranging: vaccine dose regimens for younger adults aged 18 to 55 years in Part A (Cohorts 1 to 7)

		Vaccine IM dosing regimen	Part A – Cohort numbers & dose (µg) (12 subjects per cohort)						
Vaccine / mRNA type Vaccine-encoded antigen	1 Starting dose		2	3 De-escalation dose	4	5 Optional de- escalation dose	6	7	
BNT162a1 /	RBD of the SARS-CoV-2	Prime: Day 1	1А	2A	ЗА	4A a	5А	6А	
uRNA	S protein	Boost: Day 22	3 µg b	0.6 µg a	0.1 µg	2 µg e	0.3 µg	1 µg	
BNT162b1 /	RBD of the SARS-CoV-2	Prime: Day 1	1В	2В	3В	4В	5В	6В	7В
modRNA	S protein	Boost: Day 22	10 µg	30 µg	1 µg	60 µg d	50 µg	3 µg	20 µg
BNT162b2 /	Modified version of the full	Prime: Day 1	1С	2С	3С	4С а	5C ª	6С а	7С а
modRNA	length SARS-CoV-2 S protein	Boost: Day 22	10 µg	30 µg	1 µg	60 µg d	20 μg	3 µg	50 µg
BNT162c2 / saRNA	Modified version of the full length SARS-CoV-2 S protein	Prime only: Day 1	1D 0.1 μg	2D 0.3 µg	3D 0.1 µg to <3 µg с	4D 1 μg	5D a 0.6 µg	6 D а 3 µg d	
BNT162c2 /	Modified version of the full	Prime: Day 1	1Е	2Е	3E	4E a	5Е	6Е	7Е
saRNA	length SARS-CoV-2 S protein	Boost: Day 22	0.1 µg	0.3 µg	1 µg	5-10 μg c, d	0.6 µg	3 µg	5-10 µg с, d

a) All dose escalation doses used must be judged acceptable by the Safety Review Committee (SRC) before use.

b) Status 08 JUN 2020: This cohort was set on hold by the SRC after 6 subjects had been received their Day 1 dose, furthermore the SRC decided not to perform Day 22 dosing for these 6 subjects. Due to this hold, the starting dose is also the maximum dose.

c) Specific doses to be defined, but in the range given. Already given doses will not be repeated.

d) The planned maximum doses per vaccine candidate.

e) Dosing with this vaccine variant has been put on hold. Dosing may be resumed if disease prevention data for the other vaccine candidates suggest the need for additional vaccine candidates.

IM = intramuscular; RBD = Receptor Binding Domain; S protein = SARS-CoV-2 spike protein; tbd = to be defined.

Note: Currently, dosing with BNT162a1 has been deferred. Dosing may be resumed if disease prevention data for the other vaccine candidates suggest the need for additional vaccine candidates.

BioNTech SE	Clinical Trial Protocol	Page 12 of 113
	including Amendments Nos. 01 to 09	Version: 13.0
Confidential	BNT162-01	Date: 12 JAN 2022

 Table 2:

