 Dose ranging: vaccine dose regimens for older adults aged 56 to 85 years in Part A (Cohorts 8 to 10)

		Vaccine IM dosing	Part A – Cohort numbers & dose (μg) (12 subjects per cohort) a			
Vaccine / mRNA type	Vaccine-encoded antigen	regimen	8 Older adults	9 Older adults	10 Older adults	
BNT162b1 / modRNA	RBD of the SARS-CoV-2 S protein	Prime: Day 1 Boost: Day 22	8В 10 µg	9В а 20 µg	10В а 30 µg	
BNT162b2 / modRNA	Modified version of the full length SARS-CoV-2 S protein	Prime: Day 1 Boost: Day 22	8С 10 µg	9С а 20 µg	10С а 30 µg	

a) All dose escalation doses used must be judged acceptable by the Safety Review Committee (SRC) before use.

IM = intramuscular; RBD = Receptor Binding Domain; S protein = SARS-CoV-2 spike protein.

Note: The doses planned in this trial for older adults (i.e., adults aged between 56 and 85 years) reflect clinical data from the ongoing BNT162-01 and BNT162-02 trials with the vaccine candidates BNT162b1 and BNT162b2 in younger adults (aged between 18 and 55 years) and elderly (adults aged between 65 and 85 years). For details, see the BNT162 IB.

BNT162b1:

• BNT162b1 P/B doses of 1, 10, 30, and 50 µg showed acceptable tolerability in younger adults.

• Based on the tolerability profile after the prime dose at 60 µg (BNT162-01 trial) and 100 µg (BNT162-02 trial), the respective boost doses were not administered.

• BNT162b1 P/B doses of 10, 20, and 30 µg showed acceptable tolerability in elderly adults. This tolerability appears to be better than seen in younger adults at the same doses. BNT162b2:

• BNT162b2 P/B doses of 1, 10, and 30 µg showed acceptable tolerability in younger adults.

• BNT162b2 P/B doses of 10, 20, and 30 µg showed acceptable tolerability in elderly adults. This tolerability appears to be better than seen in younger adults at the same doses.

Based on the tolerability data summarized above, and the implemented safety measures (sentinel/staggered subject dosing, post-dose observations period, wellbeing questioning, etc.) as described in the section Risk assessment, the planned doses in older subjects in this trial are expected to show acceptable tolerability. Based on the available immunogenicity data after dosing with BNT162b1 and BNT162b2 in younger adults in the BNT162-02 trial (see the BNT162 IB), the doses planned in this

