## 10.1.5 Committees - SRC

For Part A, the SRC will be comprised by a sponsor medical representative, the Medical Monitor, a sponsor-independent investigator, and a site representative.

Key roles of the SRC are as follows:

- Before progression to the next cohort, for each vaccine per cohort/dose level, assess the data, decide whether to approve initiation of the next cohort/dose level and to confirm the planned dose or define another dose for use. The data assessed by the SRC is defined in Section 1.1.
- After completing its evaluation of the 48 h data for the first 6 subjects per group in cohort, the SRC may request a prolongation of the observation period to up to Day 7 data for later cohorts or other similar adaptions to protect subject wellbeing.
- Throughout the trial, assess whether to replace trial subjects permanently discontinued due to safety issues.
- Throughout the trial, approval from the SRC will be required prior to resuming any dosing in a "stopped" cohort (see Section 6.6.1). The SRC may call for the opening of a lower dose level cohort.
- SRC may make recommendations on increasing the length of the observation periods and additional subject wellbeing calls may be included at the discretion of the SRC.

The SRC will act according to its own written procedures described in a charter, and will prepare written minutes of its meetings.

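### In dose escalation prime/boost cohorts, Section 7.1 permits boosts during the safety review of a dose limiting toxicity and does not exclude the stopped cohort, while Sections 6.6.1 and 10.1.5 require committee approval first

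*Protocol*

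**What the plan says.** Three sections of the Protocol deal with the same situation.

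- **Section 6.6.1 (Dose limiting toxicity).** If a listed event occurs while a dose escalation cohort is being enrolled, "further dosing in that cohort will be stopped". To restart: "Approval from the SRC will be required prior to any further dosing in the affected cohort".
- **Section 10.1.5 (SRC).** Throughout the trial, "approval from the SRC will be required prior to resuming any dosing in a" stopped cohort.
- **Section 7.1 (Discontinuation of trial treatment).** "IMP administration must be stopped if dose limiting toxicities described in Section 6.6.1 are observed". If so, "an unscheduled safety analysis by the SRC will be required". The next sentence reads: "Trial subjects who tolerated initial vaccinations will be allowed to receive a second vaccination during this time".

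The 7.1 permission names no cohort, dose level or vaccine as excluded, and it does not mention SRC approval.

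**The concern.** The question left open is whether a primed subject in a stopped cohort may be boosted before the SRC has decided. Sections 6.6.1 and 10.1.5 say no; Section 7.1, on its wording, says yes for anyone who tolerated the first dose. At stake is a second injection of a dose that has just been halted for safety.

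The trial has twice withheld boosts after a first dose. Footnote b to Table 1 records that the 3 µg BNT162a1 cohort was put on hold after 6 first doses: "furthermore the SRC decided not to perform Day 22 dosing for these 6 subjects". The note under Table 2 reports that, because of tolerability after the 60 µg BNT162b1 prime, "the respective boost doses were not administered". The documents do not say whether a Section 6.6.1 criterion triggered either case.

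**Working it through.** The plan gives no figure to reproduce here. The check is a comparison of text, followed by simple counting.

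**Do the rules cover the same event and the same act?**

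1. Trigger: 7.1 refers back to 6.6.1 by number, so the events are the same.
2. Period: in 7.1 the time in question is the unscheduled SRC review that those events set off. Under 6.6.1 and 10.1.5 the cohort is on hold until the SRC approves.
3. Act: 6.6.1 itself speaks of dosing with the boost when it sets the condition for BNT162c2 prime/boost cohorts. A boost therefore counts as dosing in that section.
4. Contrast: the rule in 6.6.4 on suspected unexpected serious adverse reactions limits its stop to new subjects. The dose limiting toxicity rule carries no such limit.
5. Scope: the operative sentence of 6.6.1 covers a dose escalation cohort during its enrollment. Cohorts 11 to 14 are outside it.

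**How many subjects, and how much time?**

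Inputs: 12 subjects per cohort, with the first 6 dosed before the last 6 (Section 4.1); minimum dosing on Days 1, 2 and 4 (Section 4.1 and the Schema in 1.2); boost on Day 22±2 d (Table 6, footnote h); observation periods may each be prolonged by 24 h (Section 4.1). Days are counted from the first subject's prime, and one subject's own event is taken to trigger the hold.

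First subject's boost window: 22 − 2 = Day 20 to 22 + 2 = Day 24.

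*Uncontested case: the event comes before the last six are dosed.*
- Primed subjects other than the one with the event: 6 − 1 = up to 5.
- Latest trigger Day 4: 20 − 4 = 16 days until the window opens and 24 − 4 = 20 until it closes. An earlier trigger leaves more.
- If both observation periods are prolonged by 24 h, the last six are dosed on Day 4 + 2 = 6: 20 − 6 = 14 days until it opens.

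*Contested case: an event after the last prime still counts as occurring during enrollment.*
- Subjects: 12 − 1 = up to 11.
- Trigger 7 d after the last prime, Day 4 + 7 = 11: 20 − 11 = 9 days to opening, 24 − 11 = 13 to close.
- With both prolongations, trigger on Day 6 + 7 = 13: 20 − 13 = 7 days to opening, 24 − 13 = 11 to close.

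The documents give no rate for these events, so no probability of a clash can be stated.

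**The case against.** The best defense is that the sections can be harmonised. The stop in 6.6.1 operates during enrollment, and its later paragraphs describe its purpose as guiding decisions to enroll more subjects or move to the next cohort. On that view, further dosing means dosing further subjects, and 7.1 is the specific rule for those already primed. This does not hold against the operative sentences, which speak of any dosing, nor against 6.6.1's own use of the word for boosts and the express limit to new subjects in 6.6.4. Reading 7.1 as meaning other cohorts only would be sensible, but 7.1 does not say so. If it is a deliberate exception, 6.6.1 and 10.1.5 need to state it.

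The objections to reach and size do stand:

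- De-escalation cohorts may dose all 12 subjects on one day, and the operative wording names escalation cohorts.
- The interval before the first boost window is long in the uncontested case.
- Other controls exist. The investigator may ask for an ad hoc SRC review by phone before further doses (Section 4.1). The SRC may stop an individual subject's treatment (6.6.4). Immediate concerns about a subject go to the sponsor (Section 8). These lower the risk, but they do not settle whether a stopped cohort may be boosted before approval.

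A reader might infer that subjects were boosted during a hold. The documents do not show this, and in the BNT162a1 case the SRC itself withheld the boosts. A reader might also take 11 subjects, or a margin of 7 to 13 days, as the general size of the problem. Those figures need the disputed reading of the enrollment period.

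**Conclusion.** The conflict is real and confined to dose escalation prime/boost cohorts: followed as written, 7.1 permits a boost that 6.6.1 and 10.1.5 forbid until the SRC approves. In the uncontested case it touches up to 5 primed subjects, with about 16 days or more before the first boost window opens on the minimum schedule. It takes effect only if the SRC review is long or enrollment is extended. The count assumes that a single subject's event triggers the hold.

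This is a minor point of subject protection. No estimate, analysis set or SAP analysis changes.

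**What to change.** Replace the 7.1 sentence with:

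> In a cohort stopped under Section 6.6.1, no prime or boost dose is given until the SRC approves. Subjects in other cohorts who tolerated the first dose may receive the second dose during the review.

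Add to 10.1.5:

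> When it reviews a stopped cohort, the SRC states whether pending boost doses are given, and within what window if Day 22±2 d has passed; otherwise the boost is omitted and the subject completes the SoA.

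The window clause is needed because Section 8 rules out waivers, and the delay allowance in 7.1.1 covers only Cohorts 11 to 14, for intercurrent illness. Without it, the SRC would have no stated power to release a late boost.

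The cost is one sentence replaced by two in 7.1 and one added in 10.1.5, with no new data, visits or analyses. The downside is that some boosts may be late or missed if the review is slow. Follow-up of unboosted subjects is already provided for in the notes to Table 6. The list of events in 6.6.1 and the SAP stay as they are.
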